#### Secondary efficacy analysis

As a secondary analysis we will examine the change over time of the COWS, pain VAS scores, OCS and CNSVS between groups using a mixed-effects model repeated measures (MMRM) analysis incorporating treatment period data up to 3 months. The effects in the model will include the baseline score, treatment groups, visit, treatment-by-visit interaction and baseline-by-visit interaction. Visit week will be treated as the repeated variable within a patient. Patient, treatment, and visit will be treated as class variables. Unstructured covariance matrix will be used initially, and additional types (e.g., auto- regression, Toeplitz, CS, etc.) will be tried to assess the robustness of the unstructured matrix. Comparison between treatments will be based on contrasts of least square treatment means at each week of interest. Based on the analysis above, least square means, standard errors, and 95% confidence intervals (CI) of treatment difference will be reported for the two groups.

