#### DATA MANAGEMENT

Subjects will be randomized in a 1:1 ratio to receive either active or a sham device. Randomization in blocks of 10 (5 for each treatment) will be determined using the computer program randomization.

The severity of opioid withdrawal signs and symptoms will be assessed with the COWS at several time points: 1) pre-device placement, 2) 1-hour post placement of sham or active device, 3) two hours post placement (approximately one hour after first dose of buprenorphine), 4) at subsequent follow-up in clinic on day 2 and 5) at final follow-up in clinic on day 5 prior to removal of device. The visual analogue pain and craving scale will also be administered at intervals to monitor patient comfort: 1) pre-device placement, 2) 1-hour post placement of sham or active device, 3) two hours post placement (approximately one hour after first dose of buprenorphine),4) at subsequent follow-up in clinic on day 2, 5) in clinic or remotely (via phone) on days 3 and 4, and 6) at final follow-up in clinic on day 5 prior to removal of device. Assessment of cognitive function (CNSVS) will be recorded at 1) pre-device placement, 2) 1-hour post placement of sham or active device, and 5) at final follow-up in clinic on day 5 prior to removal of device. One hour following placement of either sham or active device, the patients will be given the first dose of buprenorphine with a starting dose of 2, 4 or 8 mg at the blinded provider's discretion based on BMI, patient previous experience with BUP, patient apprehension or other factors. Adjustments to this dose will not be made for at least an hour after receiving the first dose but the providing clinician may order additional buprenorphine after one hour as indicated by initial response, previous experience, presence of precipitated clinical opioid withdrawal scale (COWS) and BMI. Subsequent adjustments will be made based on the blinded provider's discretion and patient needs and comfort as per clinic standard. Ancillary (supportive) medications to help manage signs and symptoms of opioid withdrawal will NOT be allowed for one hour after the first dose of buprenorphine. Following the first hour, symptom control medications including ibuprofen, clonidine, ondansetron, loperamide, and acetaminophen may be furnished or prescribed. A medication log will be provided to track usage of this modality. Subjects will remain blinded and keep the device on for 5 days regardless of randomization status. Subjects will be asked to return to clinic for additional induction visits based on the clinic standard of care which will be Day 2 and in some cases Days 3 & 4. In order to monitor whether neurostimulation with the BRIDGE has any added benefit for patients on outpatient opioid agonist therapy, subjects (regardless of active or placebo) will be reassessed using OCS and VAS at each subsequent visit, or remotely (via phone) when unrequired to return to clinic, during the 5-day trial.

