#### **Data Points Requiring Special Handling**

For ITT analysis, patients with multiple assessments within a scheduled visit will be included by selecting the first assessment in time within a visit. However, all data will be presented in the patient data listing.

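### The secondary MMRM is indexed by week, but every outcome it models is scheduled within Days 1 to 5, so it cannot be fitted as written or test Aim 2's time windows

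*Combined protocol and SAP*

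**What the plan says.** Secondary efficacy analysis in the combined protocol and SAP specifies one MMRM for the change over time in COWS, pain VAS, OCS and CNSVS. Four of its elements concern time:

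- Repeated factor: "Visit week will be treated as the repeated variable within a patient".
- Treatment comparison: "contrasts of least square treatment means at each week of interest".
- Data window: "incorporating treatment period data up to 3 months".
- Fixed effects: baseline score and treatment group, together with "visit, treatment-by-visit interaction and baseline-by-visit interaction". The covariance is unstructured at first, with simpler structures tried as a robustness check.

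The assessment times are in the first of the two Data Management sections (the one after Unblinding) and in the schedule table under Power Calculation:

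- COWS: before device placement, at 1 hour and at 2 hours, and then "4) at subsequent follow-up in clinic on day 2 and 5) at final follow-up in clinic on day 5 prior to removal of device".
- Pain and craving: the same first four times, and then "5) in clinic or remotely (via phone) on days 3 and 4, and 6) at final follow-up in clinic on day 5".
- Cognition: "Assessment of cognitive function (CNSVS) will be recorded at 1) pre-device placement, 2) 1-hour post placement of sham or active device", and again on Day 5.

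No section defines visit. The word also appears in Data Points Requiring Special Handling, where "patients with multiple assessments within a scheduled visit will be included by selecting the first assessment in time within a visit".

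**The concern.** Three phrases in one paragraph describe a weekly design lasting months. This trial has a five-day device period and three assessments on Day 1. The only later efficacy item is engagement in recovery treatment at 30 days, which is not an outcome of this model.

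The MMRM is the only inferential method the plan names for Aim 2 (pain, craving and cognition) and for COWS after the first hour. Specific Aims/Hypothesis states the pain and craving hypothesis for the first two hours after application and for the following 4 to 5 days. A contrast for week 1 as a whole corresponds to neither window. It would also merge the 1-hour assessment, which closes the buprenorphine-free hour, with later assessments made on buprenorphine.

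**Working it through.** **The plan's own figure.** No design calculation is given for the MMRM. The one stated calculation is for the primary t-test: 25 per group, two-sided alpha 0.049, difference 0.94 SD, at least 90% power. A noncentral t with 48 degrees of freedom gives 0.901, so the figure reproduces. Likewise 0.94 × 6 = 5.64, against the stated value of about 5.7. This is context only, because the present point does not touch that test.

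**Step 1: weeks covered.** Assume week 1 is Days 1 to 7, so that week = floor((day − 1)/7) + 1. Day 1 gives floor(0/7) + 1 = 1, and Day 5 gives floor(4/7) + 1 = 1. Every scheduled record of every outcome is in week 1.

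**Step 2: model size.** Let m be the number of levels of the visit factor. The treatment-by-visit term has m − 1 degrees of freedom. An unstructured covariance with one record per level has m(m + 1)/2 parameters. The fixed effects (intercept, baseline, treatment, visit and its two interactions) occupy 3 + 3m columns of rank 3m.

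| Factor coding | m | Treatment-by-visit df | Unstructured parameters | Columns / rank |
|---|---|---|---|---|
| COWS by assessment time (1 h, 2 h, Days 2, 5) | 4 | 3 | 4 × 5/2 = 10 | 15 / 12 |
| VAS or OCS by assessment time (1 h, 2 h, Days 2, 3, 4, 5) | 6 | 5 | 6 × 7/2 = 21 | 21 / 18 |
| CNSVS by assessment time (1 h, Day 5) | 2 | 1 | 2 × 3/2 = 3 | 9 / 6 |
| Any outcome by week | 1 | 0 | not usable (step 3) | 6 / 3 |

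The counts are per analysed score.

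**Step 3: what the literal coding does.** With one level, the rank of 3 is used up by intercept, baseline and treatment. The visit, treatment-by-visit and baseline-by-visit terms are fully aliased with them. The parameter formula assumes one record per patient per level, but here the single level holds 4, 6 or 2 records. The covariance matrix has no separate positions for them, so the unstructured form cannot be set up. The only treatment contrast left is for week 1.

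**Step 4: contrasts against the hypothesis.** Coded by assessment time, VAS and OCS each have two contrasts inside the two-hour window (1 h and 2 h) and four on Days 2 to 5. Coded by week, no contrast is specific to either window.

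**Step 5: the CNSVS count.** Design and Methods says the cognitive test is given at the same intervals as the COWS, pain and craving assessments. Data Management and the schedule table list only baseline, 1 hour and Day 5. If Design and Methods governed, m would be 4 or 6, depending on which schedule is matched. Every assessment would still fall in week 1.

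**The case against.** The best defence is that any statistician would take visit to mean the scheduled assessment time. Much of that stands. The Period row of the schedule table gives baseline, 1 hour after the device and 1 hour after buprenorphine separate columns. Data Management numbers them separately, and Efficacy Analysis refers to the respective time points. The interaction terms also make sense only with more than one level. The literal model fails visibly and would not quietly produce a wrong answer. The 3-month phrase is an upper limit that neither adds nor removes a scheduled record. What remains is that the paragraph states a different factor and different contrasts. The analyst would have to replace both when running the analysis, and Blinding and Randomization leaves the study biostatisticians unblinded.

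A reader might go further and infer lost data. Elsewhere the protocol uses visit for a day's clinic attendance. If Day 1 were one visit, the first-assessment rule in Data Points Requiring Special Handling would keep the pre-device record and discard those at 1 and 2 hours. The documents do not support that reading:

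- The rule covers ITT analysis, and ITT is the population for all efficacy analyses. The same reading would delete the 1-hour COWS that Primary Efficacy Variable names as its endpoint, and the tabulated proportion with COWS below 10 in the first hour.
- The MMRM already uses the baseline score as a covariate, so the pre-device record would not also be its Day 1 outcome.
- The schedule treats the three Day 1 assessments as distinct. The rule is naturally read as handling repeat readings at one time point.

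**Conclusion.** The point holds as a specification error in the secondary analysis. The week-based factor and contrasts conflict with a schedule that ends on Day 5. Followed literally, the model has one level, 0 degrees of freedom for treatment-by-visit, no workable unstructured covariance, and no contrast for either window of Aim 2. This goes beyond missing detail, because the analysis stated is the wrong one for the data scheduled.

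The conclusion assumes only that weeks are counted from Day 1. The CNSVS count of 2 depends on Data Management and the schedule table prevailing over Design and Methods, but the conclusion does not. No bias, loss of power or loss of records is shown. The primary one-hour comparison names its own time point and is unaffected.

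**What to change.** In Secondary efficacy analysis:

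1. Define both the visit effect and the repeated factor as the scheduled post-baseline assessment time for each instrument. For COWS these are 1 h, 2 h, Day 2 and Day 5. For VAS and OCS they are 1 h, 2 h and Days 2, 3, 4 and 5. For CNSVS they are 1 h and Day 5, subject to reconciling Design and Methods with Data Management and the schedule table.
2. Replace the weekly contrasts with treatment contrasts at each of those times.
3. Replace the 3-month limit with a window ending at Day 5.

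As a clarification only, state in Data Points Requiring Special Handling that the first-assessment rule applies within each scheduled time point.

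Make these changes before any secondary outcome is analysed by treatment group. The cost is SAP wording and one reconciliation of the CNSVS times. No patients are added. No data collection is added unless the CNSVS conflict is settled in favour of the fuller schedule in Design and Methods, which would mean more test sessions.

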#### **Missing data**

For missing data, the missing pattern will be summarized, and the subgroups investigated. Logistic regression and CART will be used to investigate the possible causes for missing data. In general, we will assume missing at random (MAR), and multiple imputations will be used for items.

To assess effects of dropouts, the dropout cohort analysis will be performed by summarizing the change of primary and secondary efficacy variables using different dropout cohorts.

#### **REPORTING ADVERSE EVENTS AND UNANTICIPATED PROBLEMS**

All safety variables (e.g., adverse events will be summarized for each assessment time (including follow-up) using descriptive statistics. Incidence of adverse events will be summarized by treatment. Overall risks/ discomforts involved are very minimal – Rare (event rate 1% - < 5%)

Possible risks/discomforts may involve:

- Discomfort upon insertion of the electrodes for < 5 minutes Rare (event rate 1% < 5%)
- Discomfort at the lead placement site > 5 minutes Rare (1 % < 5%)
- Bleeding at the electrode site if the neurovascular bundle is penetrated Rare (event rate 1% <5%)
- Localized discomfort if the electrodes should become dislodged during the wearing of the device Rare (event rate 1% < 5%)
- Localized dermatitis Rare (event rate 1% < 5%)
- Drop in blood pressure Rare (event rate 1% < 5%)
- Syncope (fainting) Rare (event rate 1% < 5%)
- Adverse effects to supporting personnel
- Skin piercing with percutaneous needles Rare (event rate 1 % < 5%)

Of note, in the recently completed neurostimulation trial for functional abdominal pain disorders in adolescents, there were no serious adverse events. The rate of reported side effects was no different between the treatment and placebo groups. Of 115 subjects, n=10 (9%) reported the following side effects: ear discomfort (n=6; three treatment/three placebo), adhesive allergy (n=3; one treatment/two placebo) and syncope due to needle phobia (n=1; placebo) (18).

#### **Safety Analysis**

The Bridge Device is FDA cleared as an aid in the treatment of opioid withdrawal symptoms. It has been classified as a class II device, with minimal no adverse effects in this population. Nevertheless, caution will be taken to monitor safety in this patient population. Safety assessments will consist of monitoring and reporting adverse events (AEs) and serious adverse events (SAEs) that are considered related to study device, all events of death, and any study specific issue of concern.

All safety variables will be summarized for each assessment time (including follow-up) by treatment group, and period using descriptive statistics. Incidence of AEs will be summarized based on body systems and preferred terms. Incidence of marked abnormal lab test results will be summarized. All safety summary outputs will be generated using the safety population.

This survey summary outputs will be generated using the sa

Exposure to Study Treatment

The following extent of exposure to study device will be summarized for each treatment group, and patient data listing will be produced:

- Overall adherence to assessment (i.e., average during the entire treatment period).
- Premature Withdrawals from the Protocol Therapy

• Patients (n,%) who prematurely withdraw from the protocol during the treatment period will be summarized separately for overall and by reason for withdrawal and will be presented in patient listing.

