#### Adverse Events

All adverse events will be summarized for the following 3 study periods separately, and include the specified AEs:

• Screening Period: Include the AEs of which the onset date is before the start of the study device placement.

• Treatment Period: Include (a) the AEs of which onset date is on or after the first day of the study device and on or prior to five days after the last device treatment day.

• Follow-up Period: Include (a) the AEs of which onset date is more than 30 days after the last device placement; OR (b) the AEs of which onset date is during the treatment period with the end date is more than 30 days after the last dose day or is unresolved and the follow up intensity is worse than the initial intensity.

For each AE recorded, the term entered by the investigator describing the event (the "verbatim term") will be assigned to a standardized term (the "preferred term") based on the Medical Dictionary for Regulatory Activities (MedDRA) dictionary. Within this dictionary, all preferred terms are grouped into categories known as "system organ class" terms or "super class" terms (SCT). All data displays of AE will be performed using the preferred terms and super-class terms (also referred as Body System).

For each treatment group, the frequency of each AE preferred term will be defined as the number of patients reporting at least one occurrence of the event. The incidence rate will be calculated as the frequency count divided by the total number of patients in the population and treatment group specified. Each table will also present the overall number of patients experiencing at least one AE and the total number of adverse events reported.

In the summary table of AEs by intensity, if a patient has more than one occurrence of an event, the event with the most severe intensity will be counted. If the intensity of an adverse event is missing, then the AE will be included only in the total number of events columns, and not in the count of patients with the event by intensity. In the summary table of AEs by relationship to trial treatment, if a patient has more than one occurrence of an event, the most closely related event will be counted. If the relationship of an adverse event is missing, then the AE will be included only in the total number of events columns, and not in the count of patients with the event by relationship.

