#### Serious Adverse Events

The PI, within 24 hours, will report all serious adverse events occurring in any enrolled subjects to the IRB. Unexpected (but not serious) adverse events occurring in enrolled subjects which, in the opinion of the PI, are possibly related to participation in the study will be reported by the PI within 5 working days to the IRB. Enrollment will be discontinued after reaching 50 subjects.

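### The Safety Analysis section limits AE and SAE monitoring to events considered device-related, which contradicts the all-AE tables and all-SAE reporting planned elsewhere; if it governs recording, non-serious AEs judged unrelated would be missing

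*Combined protocol and SAP*

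**What the plan says.** The scope of safety data is set out in the Safety Analysis section, which has safety assessment consist of monitoring and reporting "adverse events (AEs) and serious adverse events (SAEs) that are considered related to study device". Two exceptions follow, "all events of death, and any study specific issue of concern".

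Other sections assume a wider scope:

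- Reporting Adverse Events and Unanticipated Problems: "Incidence of adverse events will be summarized by treatment". No relatedness condition is attached.
- Adverse Events: "All adverse events will be summarized for the following 3 study periods separately". For the screening period the instruction is "Include the AEs of which the onset date is before the start of the study device placement".
- Adverse Events also gives counting rules that begin "In the summary table of AEs by relationship to trial treatment". An event whose relationship is missing still counts in the total number of events.
- The closing text of Adverse Events says that the listing of patients who leave because of an AE is to show every AE they reported, not only the one that led to withdrawal.
- Serious Adverse Events: within 24 hours the PI "will report all serious adverse events occurring in any enrolled subjects to the IRB".

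**The concern.** A table can show only what was recorded. The Safety Analysis sentence makes a relatedness judgement the entry condition for the safety data, whereas the tables treat relatedness as one attribute of events already in the data. An event screened out at the bedside cannot be recovered at analysis.

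Attribution is difficult in this trial. Patients are in active withdrawal, buprenorphine follows one hour after placement, and clonidine and other symptom medication are allowed an hour after that (Data Management). The plan lists a fall in blood pressure and syncope as possible device risks, and either could reasonably be put down to withdrawal or a drug. In the earlier adolescent trial that the plan cites, the one syncope occurred in a placebo patient and was attributed to needle phobia. Whether such an event would be captured under a device-related filter depends on one person's judgement. No data safety monitoring board is planned unless requested, so the by-arm AE summary is a main source of comparative safety information.

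**Working it through.** The plan states no figure on this point, so the check is a comparison of texts.

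**Step 1. Can the narrow scope supply the planned outputs?**

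| Planned output | What it needs | What the Safety Analysis scope supplies |
|---|---|---|
| All AEs by period | Every AE | Device-related AEs, deaths, issues of concern |
| Screening-period AEs | Events before placement | Nothing apart from those two exceptions, since an event before placement cannot be caused by the device |
| AEs by relationship | Events at every level of relationship | Essentially the related level only |
| All AEs in patients withdrawing for an AE | Every AE in those patients | The related ones |
| All SAEs to the IRB | Every SAE | Device-related SAEs and deaths |

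None of the five can be produced in full under the narrow scope.

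**Step 2. Does a different reading of the sentence remove the conflict?** The relatedness clause could be attached to SAEs alone. The plan would then follow all AEs but only related SAEs, which is less coherent and still contradicts the Serious Adverse Events section. That deaths are listed separately and without restriction suggests the clause is meant to limit both AEs and SAEs.

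**Step 3. Does another section settle what is recorded?** The Adverse Events section describes how recorded events are coded and counted, not which events to record. As it reads in the available text, the schedule of assessments has no AE row. The efficacy and demographic items under Data to be collected include no AE item. The Safety Monitoring Plan refers back to the earlier text for how side effects are documented. The Safety Analysis sentence is therefore the most explicit statement of scope.

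**Step 4. What would the by-arm comparison lose?** Let p_A and p_S be the true proportions of patients with an AE on active and sham, and r_A and r_S the shares of those patients with an event judged device-related. The recorded difference is

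r_A·p_A − r_S·p_S.

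- If the shares are equal (r_A = r_S = r), this is r·(p_A − p_S). The difference shrinks, but a true zero stays zero. The summary is incomplete without being biased towards either arm.
- If the shares differ because the assessor has guessed the allocation, a recorded difference can appear even when p_A = p_S. Its direction cannot be predicted: an assessor who believes the device is active may be readier to blame it, or readier to excuse it.

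The second case needs a route to unblinding. One exists: the placement instructions tell patients that they may feel pulsing or warmth, and the sham delivers no current. The documents do not show that this reveals allocation to the person judging relatedness.

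**Step 5. Can the loss be sized?** No. The only AE frequency observed in a trial that the documents report is 10 of 115 (10/115 = 8.7%, given as 9%) in adolescents with abdominal pain, without a split by relatedness. Any value for r would be an assumption.

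**The case against.** The strongest reply is that this is one loosely worded summary sentence and that the operational text points to recording everything. The tables cover all AEs, the withdrawal listing shows all AEs, and SAEs go to the IRB whatever their cause. The rule that keeps events with a missing relationship in the totals makes little sense if relatedness were a condition of entry. This carries weight. It means that the loss is conditional on which text the staff follow, but it does not tell them which one to follow.

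It can also be said that withdrawal symptoms are captured anyway. COWS is taken in both arms on days 1, 2 and 5, and buprenorphine dosing and symptom medication are logged. That stands for much of the withdrawal picture. It does not extend to syncope, which COWS does not score, or to blood pressure, since the schedule shows vital signs at baseline only.

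The sentence might be meant as a rule on what goes to the IRB. But it covers monitoring as well as reporting, and IRB reporting has its own rules, which for SAEs carry no relatedness condition.

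A reader might infer that SAEs and deaths would be lost. The documents do not support that: the Serious Adverse Events section requires every SAE to be reported, and the Safety Analysis sentence itself keeps all deaths and issues of concern. A reader might also infer that the safety comparison is biased as planned. Providers, nurses and all coordinators except the unblinded lead are to be blinded, and a relatedness judgement made blind narrows the comparison without favouring an arm.

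**Conclusion.** The contradiction is established by the text and does not depend on any assumption. The Safety Analysis scope conflicts with the all-AE, screening-period and by-relationship tables, with the withdrawal listing, and with the SAE reporting rule.

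The consequence is conditional. If the narrow scope governs recording, non-serious AEs judged unrelated would be missing, the screening-period table would be empty apart from any death or issue of concern, the by-relationship table would hold essentially related events only, and the AE incidence by arm would be incomplete. If the all-AE text governs, the data would be complete and only the wording is at fault. Bias between arms is a further possibility that also requires device sensation to have revealed allocation to those judging relatedness.

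The by-arm safety summary is descriptive, with no formal test stated, and the primary efficacy analysis is unaffected. The size of any loss cannot be estimated from the documents. The point should be corrected because an unrecorded event cannot be restored later and the correction is cheap.

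**What to change.** Reconcile the Safety Analysis, Adverse Events and Serious Adverse Events sections to one scope. In Safety Analysis, replace the device-related restriction with a statement such as: all AEs and SAEs will be collected from consent to the end of study follow-up, whatever their relationship to the device, and the relationship will be recorded for each event. The by-relationship table can then stand as planned.

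The same edit should state when follow-up ends for AE collection. In the Adverse Events section the treatment period closes five days after the last device day, while new events enter the follow-up period only when they start more than 30 days after the last placement. An event that starts in between falls in neither period. One substituted sentence does not resolve this, so the period definitions need to be aligned with it.

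The cost of the scope change is one sentence and slightly more AE recording in a 50-patient, single-centre trial. Sample size, visits and the efficacy analysis do not change.
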